# 7.6.2.3 Other Secondary Efficacy Endpoints

Descriptive statistics for the other secondary efficacy endpoints will be presented by treatment group and by study visit where appropriate.

For time-to-event endpoints, similar methods will be used as specified for the analyses of the primary variable. For binary endpoints, the treatment group comparisons will be performed at Day 8 only, with descriptive statistics provided for each clinic visit.

• Percentage of patients in each study group who require hospital re-admission related to COVID-19 through Day 31.

The percentage of patients who require re-admission for COVID-19 related signs or symptoms through Day 31 will be presented by treatment group and Clopper–Pearson 95% CI will be computed for the binomial proportion.

Only patients who discharged from the hospital will be included in the analysis of the re-admission for COVID-19 related signs or symptoms.

• Percentage of patients in each study group and in each of the categories of the 11-point WHO Clinical Progression Scale on Days 4, 8, 15, and 31.

The clinical status, as assessed on the 11-point WHO Clinical Progression Scale will be summarised on Days 4, 8, 15, and 31, by treatment group.

In case of missing clinical status at the time point, the following approach will be used:

- If patient dies before or on the time point → clinical status = 10.
- Otherwise, LOCF approach will be used, where the last recorded clinical status for the same patient is carried forward to the missing clinical status at the time point.
- Percentage of patients in each study group requiring oxygen therapy on Days 4, 8, 15, and 31.

The percentage of patients who require oxygen therapy on Days 4, 8, 15, and 31, will be presented by treatment group. Clopper–Pearson 95% CI will be computed for the binomial proportions.

If a patient requires any change in the oxygen therapy on Day 4, 8, 15, or 31, the new oxygen status will be selected, e.g. if a patient changes from "Low-flow" to "No supplemental oxygen needed" on Day 4, "Require oxygen therapy on Day 4'' = No. On the other hand, if a patient changes from "No supplemental oxygen needed" to "Low-flow" on Day 8, "Require oxygen therapy on Day 8" = Yes.

The difference in the percentage of patients who require oxygen therapy on Days 4, 8, 15, and 31 between each dose of plitidepsin versus control arm

will be presented for each dose of plitidepsin and the exact 95% CI will be computed for the difference in the percentage.

The oxygen therapy rate on Day 8 between each dose of plitidepsin versus control arm will be compared using a stratified logistic regression model. The model will be adjusted for the randomisation stratification factors. The odds ratios, 95% CIs, and 2-sided p-values for the comparison of each dose of plitidepsin versus control arm will be presented.

Moreover, the percentage of patients who require oxygen therapy at some time from Day 1 to Day 4, from Day 1 to Day 8, from Day 1 to Day 15, and from Day 1 to Day 31, will be presented by treatment group. Clopper– Pearson 95% CI will be computed for the binomial proportions.

The difference in the percentage of patients who require oxygen therapy at some time during each period between each dose of plitidepsin versus control arm will be presented for each dose of plitidepsin and the exact 95% CI will be computed for the difference in the percentage.

The percentage of patients who require oxygen therapy at some time from Day 1 to Day 8 between each dose of plitidepsin versus control arm will be compared using a stratified logistic regression model. The model will be adjusted for the randomisation stratification factors. The odds ratios, 95% CIs, and 2-sided p-values for the comparison of each dose of plitidepsin versus control arm will be presented.

• *Time to intensification of respiratory support (WHO >6 [intubation]).* 

Time to intensification of respiratory support (in days), defined as the first day, from randomisation through completion of the study, on which a patient satisfies a category > 6 on the 11-point WHO Clinical Progression Scale.

Patients who reported a category > 6 on the 11-point WHO Clinical Progression Scale or died due to any cause through the study will be considered as an event on the first day on which a patient satisfies a category > 6 on the 11-point WHO Clinical Progression Scale or date of death, whichever occurs first. Otherwise, patients will be censored at the date of the last visit or telephone contact with the patient.

Time-to intensification of respiratory support (days) = (date of event or censoring – date of randomisation)

If date of event is the same as the randomisation date then time-to intensification of respiratory support will be considered as 1 day. If no data is available then time will be censored at time 0.

CONFIDENTIAL

Time-to intensification of respiratory support will be analysed using the Kaplan-Meier method and 25th percentile, median and 75th percentile time will be presented by treatment group together with 95% CIs. The 95% CIs will be computed based on Brookmeyer-Crowley method and using a log log transformation. The mean time to intensification of respiratory support and its standard error will be also presented by treatment group.

Time-to intensification of respiratory support between each dose of plitidepsin versus control arm will be compared using a stratified log-rank test, including the randomisation stratification factors as covariates, ie, Geographical Region (Europe vs. Rest of the World), Charlson Comorbidity index (0-1 vs. >1) and pre-baseline Barthel index ( $\geq$ 90 versus <90) as derived using the eCRF data. The 2-sided p-values for the comparison of each dose of plitidepsin versus control arm will be presented.

A stratified Cox proportional-hazards regression model, including the randomisation stratification factors as covariates, will be applied to compare results between each dose of plitidepsin versus control arm. Hazard ratios, 95% CIs, and 2-sided p-values for the comparison of each dose of plitidepsin versus control arm will be presented. The cumulative survival will be displayed graphically by treatment group using a Kaplan-Meier curve.

• Total duration of ICU stay for each study group.

The total duration of ICU stay (in days), defined as the number of days in ICU

Duration of ICU stay (days) = (last date in ICU – date of admission in ICU) + 1 – off-ICU days

The number and percentage of patients who were admitted in ICU together with the total duration of ICU stay (in days) will be summarised by treatment group.

Only patients who were admitted in ICU will be included in the analysis of the duration of ICU stay.

• Percentage of patients in each study group requiring high-flow oxygen on Days 4, 8, 15, and 31.

The percentage of patients who require high-flow oxygen on Days 4, 8, 15, and 31, will be presented by treatment group. Clopper–Pearson 95% CI will be computed for the binomial proportions.

Similarly, this endpoint will be analyzed as oxygen therapy rate.

• Percentage of patients in each study group requiring non-invasive mechanical ventilation on Days 4, 8, 15, and 31.

The percentage of patients who require non-invasive mechanical ventilation on Days 4, 8, 15, and 31, will be presented by treatment group. Clopper– Pearson 95% CI will be computed for the binomial proportions.

Similarly, this endpoint will be analyzed as oxygen therapy rate.

• Percentage of patients in each study group requiring invasive mechanical ventilation or ECMO on Days 4, 8, 15, and 31.

The percentage of patients who require invasive mechanical ventilation or ECMO on Days 4, 8, 15, and 31, will be presented by treatment group. Clopper–Pearson 95% CI will be computed for the binomial proportions.

Similarly, this endpoint will be analyzed as oxygen therapy rate.

• Time to initiation with immune-modulating drugs.

Time to initiation with immune-modulating drugs, defined as the first day, from randomisation through completion of the study, on which a patient receives subsequent immune-modulating drugs.

Patients who started subsequent immune-modulating drugs will be considered as an event on the first date of starting a subsequent immunemodulating drug. Otherwise, in case of early study discontinuation due to any reason the patient will be censored at the date of the early study discontinuation. Otherwise, the patient will be censored at the date of the Day 31 visit or death date, whichever is first.

Time-to initiation with immune-modulating drugs (days) = (date of event or censoring – date of randomisation)

If date of event is the same as the randomisation date then time-to initiation with immune-modulating drugs will be considered as 1 day. If no data is available then time will be censored at time 0.

Time-to initiation with immune-modulating drugs will be analysed using the Kaplan-Meier method and 25th percentile, median and 75th percentile time will be presented by treatment group together with 95% CIs. The 95% CIs will be computed based on Brookmeyer-Crowley method and using a log log transformation. The mean time to initiation with immune-modulating drugs and its standard error will be also presented by treatment group.

Time-to initiation with immune-modulating drugs between each dose of plitidepsin versus control arm will be compared using a stratified log-rank test, including the randomisation stratification factors as covariates, ie, Geographical Region (Europe vs. Rest of the World), and Charlson Comorbidity index (0-1 vs. >1) and pre-baseline Barthel index ( $\geq$ 90 versus

<90) as derived using the eCRF data. The 2 sided p values for the comparison of each dose of plitidepsin versus control arm will be presented.

A stratified Cox proportional-hazards regression model, including the randomisation stratification factors as covariates, ie, Geographical Region (Europe vs. Rest of the World), and Charlson Comorbidity index (0-1 vs. >1) and pre-baseline Barthel index ( $\geq$ 90 versus <90) as derived using the eCRF data, will be applied to compare results between each dose of plitidepsin versus control arm. Hazard ratios, 95% CIs, and 2-sided p-values for the comparison of each dose of plitidepsin versus control arm will be presented.

The cumulative survival will be displayed graphically by treatment group using a Kaplan-Meier curve.

• Time to initiation with antiviral drugs.

Time to initiation with antiviral drugs, defined as the first day, from randomisation through completion of the study, on which a patient receives subsequent antiviral drugs.

Patients who started subsequent antiviral drugs will be considered as an event on the first date of starting a subsequent antiviral drug. Otherwise, in case of early study discontinuation due to any reason the patient will be censored at the date of the early study discontinuation. Otherwise, the patient will be censored at the date of the Day 31 visit or death date, whichever is first.

Time-to initiation with antiviral drugs (days) = (date of event or censoring – date of randomisation)

If date of event is the same as the randomisation date then time-to initiation with immune-modulating drugs will be considered as 1 day. If no data is available then time will be censored at time 0.

Similarly, this endpoint will be analyzed as time to initiation with immunemodulating drugs.

• Percentage of patients receiving subsequent immune-modulating drugs on Days 4, 8, 15, and 31.

The percentage of patients receiving immune-modulating drugs at some time from Day 1 to Day 4, from Day 1 to Day 8, from Day 1 to Day 15, and from Day 1 to Day 31 will be presented by treatment group. Clopper–Pearson 95% CI will be computed for the binomial proportions.

Similarly, this endpoint will be analyzed as ICU admission rate.

• Percentage of patients receiving subsequent antiviral drugs on Days 4, 8, 15, and 31.

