#### 2.1.3.3 Other Secondary Objectives

The other efficacy secondary objectives of this study are

- To compare efficacy of plitidepsin 1.5 mg or 2.5 mg versus the control in terms of hospital readmission related to COVID-19.
- To compare efficacy of plitidepsin 1.5 mg or 2.5 mg versus the control in terms of clinical evolution.
- To compare efficacy of plitidepsin 1.5 mg or 2.5 mg versus the control in terms of the need of supplementary oxygen.
- To compare efficacy of plitidepsin 1.5 mg or 2.5 mg versus the control in terms of the need of intensification of respiratory or intensive care support.
- To compare efficacy of plitidepsin 1.5 mg or 2.5 mg versus the control in terms of the need of intensification of pharmacological therapies.
- To compare efficacy of plitidepsin 1.5 mg or 2.5 mg versus the control in terms of superinfections.
- To compare efficacy of plitidepsin 1.5 mg or 2.5 mg versus the control in terms of mortality.
- To compare efficacy of plitidepsin 1.5 mg or 2.5 mg versus the control in terms of the evolution of viral load.
- To compare efficacy of plitidepsin 1.5 mg or 2.5 mg versus the control in terms of the evolution of inflammatory markers.
- To compare efficacy of plitidepsin 1.5 mg or 2.5 mg versus the control in terms of the immune response against severe acute respiratory syndrome coronavirus 2 (SARS-CoV-2).
- To compare efficacy in the primary endpoint and describe safety/tolerability of pooled plitidepsin arms versus control.
- To compare efficacy in the primary endpoint and describe safety/tolerability between plitidepsin arms (1.5 versus 2.5 mg) in case both are significantly superior to the control.
- To explore the influence of risk factors or scores for clinical deterioration that were not individually included.
- To compare the results obtained before and after the change of the primary and key secondary endpoint (protocol v.6 versus v.7).

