## **3.5 Other Secondary Endpoints**

The other secondary endpoints are:

- Percentage of patients in each study group who require hospital readmission related to COVID-19 through Day 31.
- Percentage of patients in each study group and in each of the categories of the 11-point WHO Clinical Progression Scale on Days 4, 8, 15 and 31.
- Percentage of patients in each study group requiring oxygen therapy on Days 4, 8, 15 and 31.
- Time to intensification of respiratory support (WHO >6 [intubation]).

- Total duration of ICU stay for each study group.
- Percentage of patients in each study group requiring high-flow oxygen on Days 4, 8, 15, and 31.
- Percentage of patients in each study group requiring non-invasive mechanical ventilation on Days 4, 8, 15 and 31.
- Percentage of patients in each study group requiring invasive mechanical ventilation or ECMO on Days 4, 8, 15, and 31.
- Time to initiation with immune-modulating drugs.
- Time to initiation with antiviral drugs.
- Percentage of patients receiving subsequent immune-modulating drugs on Days 4, 8, 15 and 31.
- Percentage of patients receiving subsequent antiviral drugs on Days 4, 8, 15 and 31.
- Percentage of patients in each study group with nosocomial infection by Days 4, 8, 15 and 31.
- Mortality in each study group on Days 4, 8, 15 and 31.
- Change in the viral load of SARS-CoV-2 in each study group from Day 1 before administration of the study drug until Day 8.
- Percentage of patients in each study group with undetectable viral load of SARS-CoV-2 on Day 8.
- Change in inflammatory biomarkers (C- reactive protein [CRP], ferritin, interleukin [IL]-6, IL-1 $\beta$ , IL-10 and tumour necrosis factor alpha [TNFa]) in each study group from baseline until Days 2, 3, 4, 8, and 31.
- Change respect to baseline in individual serological assessments.
- Time to sustained withdrawal of supplementary oxygen (11-category WHO Clinical Progression Scale ≤4) with no subsequent reutilisation during remaining study period, before (protocol v.6) and after the amendment (protocol v.7).
- Time to sustained (ie, with no subsequent readmission to Day 31) hospital discharge (since randomisation), before (protocol v.6) and after the amendment (protocol v.7).
- Obesity, hypertension, age and individual co-morbidities included in the Charlson Index (Appendix 11- Age-adjusted Charlson Index), ISARIC-4C score (Appendix 14 - ISARIC 4C Mortality & 4C Deterioration Scores), or vaccination status.

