The percentage of patients who require admission to ICU at some time from Day 1 to Day 4, from Day 1 to Day 8, from Day 1 to Day 15, and from Day 1 to Day 31 will be presented by treatment group. Clopper–Pearson 95% CI will be computed for the binomial proportions.

The difference in the percentage of patients who require admission to ICU at some time during each period between each dose of plitidepsin versus control arm will be presented for each dose of plitidepsin and the exact 95% CI will be computed for the difference in the percentage.

The percentage of patients who require admission to ICU at some time from Day 1 to Day 8 between each dose of plitidepsin versus control arm will be compared using a stratified logistic regression model. The model will be adjusted for the randomisation stratification factors. The odds ratios, 95% CIs, and 2-sided p-values for the comparison of each dose of plitidepsin versus control arm will be presented.

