• Change respect to baseline in individual serological assessments.

The percentage of patients with a serologic response anti-SARS-CoV-2 at Day 31 will be presented by treatment group. Clopper–Pearson 95% CI will be computed for the binomial proportions.

The Baseline value for the serologic response anti-SARS-CoV-2 is defined as the immunoglobulin (Ig)G Antibodies quantification value collected at the time of the clinic visit on Day 1.

Patients are considered to have a serologic response anti-SARS-CoV-2 if:

- Baseline IgG Antibodies quantification is interpreted as negative (e.g. <0.8), borderline (e.g. ≥0.8 and <1.1) or missing and increases above the established boundary (e.g. ≥1.1), following study drug administration.

- Baseline IgG Antibodies are positive and the result at Day 31 sample is at least two-folds greater than the baseline sample.

All of the other options are considered as non-serologic response.

Cutoffs for IgG Antibodies quantification will be selected at the analysis time based on the latest available specifications of the selected technology.

The difference in the percentage of patients with a serologic response anti-SARS-CoV-2 between each dose of plitidepsin versus control arm will be presented for each dose of plitidepsin and the exact 95% CI will be computed for the difference in the percentage.

The percentage of patients with a serologic response anti-SARS-CoV-2 between each dose of plitidepsin versus control arm will be compared using a stratified logistic regression model. The model will be adjusted for the randomisation stratification factors. The odds ratios, 95% CIs, and 2-sided pvalues for the comparison of each dose of plitidepsin versus control arm will be presented.

The IgG Antibodies quantification values at baseline and at Day 31 visit, and the change from Baseline in IgG Antibodies quantification values will be summarized using standard descriptive statistics.

The percent change in IgG Antibodies quantification from Baseline at Day 31 visit will be defined as:

% change from Baseline = 100\*(Day 31 value – Baseline value)/Baseline Value

Data from all study visits, scheduled and unscheduled, will be listed.

• To compare efficacy in the primary endpoint and describe safety/tolerability of pooled plitidepsin arms versus control.

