## Table 14.2.3.4 Re-Admission for COVID-19 Related Signs or Symptoms (Full Analysis Set)

Variable	Plitidepsin 2.5mg	Plitidepsin 1.5mg	Control Arm
	(N=XXX)	(N=XXX)	(N=XXX)
Patients who Discharged from the Hospital	XXX	XXX	XXX
Re-admission for COVID-19 Related Signs or Symptoms, n (%)	xxx (xx.x)	xxx (xx.x)	xxx (xx.x)
95% CI for Re-admission for COVID-19 Related Signs or Symptoms (%) [a]	xx.x - xx.x	xx.x - xx.x	xx.x - xx.x
Non Re-admission for COVID-19 Related Signs or Symptoms, n (%)	xxx (xx.x)	xxx (xx.x)	xxx (xx.x)

N = number of patients in analysis set; n = number of patients in each category. % = percentages are calculated based on the number of patients who discharged from the hospital within each treatment group. CI = Confidence interval.

[a] Clopper-Pearson 95% confidence interval. Reference: Listing 16.2.6.3

Programming notes (not part of the table):

• Table template TEF009A.

• The displayed xxx do not reflect actual decimal precision. Please follow Section 2.11 for rounding rules.

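### COVID-19 readmission is an objective to be compared with control, but the SAP plans only within-arm percentages among discharged patients and no between-arm estimate (minor)

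*SAP*

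**What the plan says.** The objective in SAP section 2.1.3.3 is comparative: "To compare efficacy of plitidepsin 1.5 mg or 2.5 mg versus the control in terms of hospital readmission related to COVID-19". Section 3.5 defines the endpoint as "Percentage of patients in each study group who require hospital readmission related to COVID-19 through Day 31".

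For the analysis, section 7.6.2.3 says that the percentage "through Day 31 will be presented by treatment group and Clopper–Pearson 95% CI will be computed for the binomial proportion". The denominator is stated in the same place ("Only patients who discharged from the hospital will be included in the analysis of the re-admission") and repeated in the footnote of Table 14.2.3.4: "percentages are calculated based on the number of patients who discharged from the hospital within each treatment group". The rows of that shell are the number discharged, readmitted n (%), its 95% CI, and not readmitted n (%).

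The opening of section 7.6.2.3 gives the general rule: "For binary endpoints, the treatment group comparisons will be performed at Day 8 only".

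**The concern.** The objective asks whether readmission differs between arms, and no planned output estimates that difference. The reader is left to compare separate intervals by eye.

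The percentages also do not compare randomised groups. Being discharged is an outcome of treatment, and follow-up stops at a fixed study day, not a fixed time after discharge. A patient discharged on Day 5 can be readmitted over 26 days (31 − 5); one discharged on Day 28 has 3 (31 − 28). If one arm discharges sooner, its discharged patients are observed for longer.

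At stake is a secondary question: whether COVID-19 readmission differs between arms, as a complement to the discharge result.

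**Working it through.** **Step 1: is the missing contrast a rule or an exception?** Setting the binary endpoints of sections 7.6.2.2 and 7.6.2.3 side by side:

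| Endpoint | Difference against control with exact CI | Model-based odds ratio |
|---|---|---|
| ICU admission (Table 14.2.3.3) | every period, including Day 1 to 31 | Day 1 to 8 |
| Nosocomial infection (Table 14.2.3.16.1) | every period, including Day 1 to 31 | Day 1 to 8 |
| Serologic response (Table 14.2.3.21.1) | Day 31 | Day 31 |
| COVID-19 readmission (Table 14.2.3.4) | none | none |

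For ICU admission the text says that "the exact 95% CI will be computed for the difference in the percentage", and Table 14.2.3.3 carries this row at Days 4, 15 and 31 as well as Day 8. For serologic response, assessed at Day 31, the SAP says that the "percentage of patients with a serologic response anti-SARS-CoV-2 between each dose of plitidepsin versus control arm will be compared". So the Day 8 rule does not stop the plan from giving differences at other times. Readmission is defined only through Day 31, so the rule gives it nothing.

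**Step 2: how large is the effect of unequal time at risk?** The SAP gives no discharge median, discharge hazard ratio or readmission rate, so there is no planned figure to reproduce. The inputs below are assumptions:

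- time to discharge exponential, control median m = 8, 10 or 12 days; the 8 and the hazard ratio 1.4 are borrowed from the oxygen-withdrawal hypothesis in section 2.3 (8 / 1.4 = 5.71, consistent with the 5.7 days given there);
- the same constant daily readmission hazard h after discharge in both arms, so no true difference; deaths ignored.

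With λ = ln 2 / m, mean time at risk among discharged patients is 31 / (1 − e^(−31λ)) − 1/λ.

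- Control, m = 8: λ = 0.0866, 1 − e^(−31λ) = 0.9318, giving 33.27 − 11.54 = 21.7 days.
- Faster arm, m = 5.71: λ = 0.1213, 1 − e^(−31λ) = 0.9767, giving 31.74 − 8.24 = 23.5 days.

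The readmission percentage among all patients is ∫₀³¹ λe^(−λt)(1 − e^(−h(31−t))) dt. Dividing by 1 − e^(−31λ) gives the percentage among discharged patients.

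| Medians (control / faster) | h per day | Among discharged | Ratio | Among all patients | Ratio |
|---|---|---|---|---|---|
| 8 / 5.71 | 0.002 | 4.24% vs 4.58% | 1.08 | 3.95% vs 4.48% | 1.13 |
| 8 / 5.71 | 0.004 | 8.28% vs 8.94% | 1.08 | 7.72% vs 8.73% | 1.13 |
| 10 / 7.14 | 0.004 | 7.89% vs 8.50% | 1.08 | 6.97% vs 8.08% | 1.16 |
| 12 / 8.57 | 0.004 | 7.60% vs 8.15% | 1.07 | 6.33% vs 7.49% | 1.18 |

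Over h = 0.001 to 0.005 and all three medians, the discharged-only gap is 0.15 to 0.81 points.

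**Step 3: early readmissions.** If risk is confined to 7 days after discharge, 31 − t is replaced by min(31 − t, 7). The discharged-only ratio falls to 1.014–1.017.

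**Step 4: precision.** The 95% half-width for a difference is about 1.96 × √(2p(1 − p)/n). At p = 5% it is 4.2 points with 203 per arm (the planned size) and 7.8 points with 60 per arm. The 60 is an assumption, prompted by section 8: recruitment stopped before 33% of events, and section 7.8 puts that at 175 over three arms, or about 58 per arm. With 3 readmitted of 60, a within-arm Clopper–Pearson interval runs from 1.0% to 13.9%.

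**The case against.** Comparative wording is used throughout section 2.1.3.3, including for inflammatory markers, which the SAP only describes. Leaving a sparse post-discharge event descriptive is a defensible choice for an other-secondary endpoint. That stands as a reason to rate the point low. It does not explain why the other admission and infection endpoints get a difference and this one does not.

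Three stronger readings are tempting, and the documents do not support them.

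- **That premature discharge goes unchecked.** The key secondary endpoint is sustained discharge, with no readmission to Day 31. It is compared in the ITT population by stratified log-rank test with a supportive Cox model (section 7.6.2.1). A discharge followed by readmission is not an event at that discharge. The exploratory complete-recovery analysis carried over from protocol version 6 also requires no COVID-19 readmission. Neither isolates the readmission rate, but the harm is narrower than it first looks.
- **That patients never discharged vanish from the table.** Table 14.2.3.4 shows N and the number discharged, so the remainder can be read off. What cannot be read off is how many of them died and how many were still in hospital. Mortality has its own compared analysis.
- **That the percentages are seriously tilted against a faster arm.** Step 2 gives under 1 point, well inside sampling error, and only if discharge times differ.

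It is also fair to say that an all-FAS difference alone does not cure the tilt. In the same model its ratio is larger (1.13 to 1.18), because a faster arm has more patients discharged and so exposed. And with few patients, a difference will be imprecise, which is not a fault of the plan.

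**Conclusion.** The point holds as a gap between objective and analysis. Readmission is to be compared with control, and neither section 7.6.2.3 nor Table 14.2.3.4 produces a between-arm estimate. This rests on the text alone.

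The post-randomisation denominator and unequal time at risk are real but small: about 7–8% relative and under 1 point with a constant hazard and a discharge hazard ratio of 1.4, and about 1–2% relative if risk is confined to the first week. Those sizes depend on assumed rates that the SAP does not give. They justify a note beside the table, not a claim of material bias.

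This is a minor improvement to an other-secondary endpoint. Primary and key secondary conclusions are unaffected.

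**What to change.** In section 7.6.2.3 and Table 14.2.3.4:

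- Add the difference in the readmission percentage for each plitidepsin dose against control, with exact 95% CI, in the format of Table 14.2.3.3, on all FAS patients.
- Show it beside rows for discharged and not readmitted, readmitted for COVID-19, still in hospital at Day 31, and died without readmission. A higher readmission count can then be read against more patients discharged.
- Keep the discharged-only percentage as a descriptive line, with a note that time at risk to Day 31 differs when discharge times differ.
- Optionally, add the percentage readmitted within a fixed window after discharge (for example 7 days), which would largely remove that difference.

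The cost is a few table rows from data already listed (Listing 16.2.6.3 for hospital status). The downside is one more exploratory comparison, which will be imprecise.
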